8.1. Other changes in the SAP

Solicited event	Lower level term code	Corresponding Lower level term decode
Erythema	10022061	Injection site erythema
Fever	10016558	Fever

Solicited events will be coded by MedDRA as per the following codes:

The aim is to align the lower level term in the SAP with the coding done in CE domain in SDTM.

Clarification on how age at first dose in years will be computed (see section 10.1.3.1)

Clarification on how duration of events will be calculated (see section 10.1.3.6).

Clarification on counting rules for combining grade 3 solicited and unsolicited adverse events (see section 10.1.3.7)
9. NON-STANDARD DATA DERIVATION RULES AND STATISTICAL METHODS

The following sections describe additional derivation rules and statistical methods which are not presented in section 10.1 (Business rules for standard data derivations and statistical methods).

9.1. Handling of missing data

9.1.1. Dates

When partially completed dates (i.e. with missing day or month) are used in calculations, the following rules will be applied:

- Adverse event start dates with missing day:
 - If the month is not the same as the vaccine dose, then the imputed start date will be the 1st of the month
 - If the event starts in the same month as the vaccine dose, the flag indicating if the event occurred before or after vaccination (AE.AESTRTPT) will be used to complete the date. If 'after vaccination' is selected, the imputed start date will match the vaccine dose given during that month. If 'before vaccination' is selected, the imputed date will be one day before the vaccine dose given during that month.
- Adverse event start dates with missing day and month:
 - If the year is not the same as the vaccine dose, then the imputed start date will be the 1st of January.
 - If the event starts in the same year as the vaccine dose, the flag indicating if the event occurred before or after vaccination (AE.AESTRTPT) will be used to complete the date. If 'after vaccination' is selected, the imputed start date will match the first vaccine dose given during that year. If 'before vaccination' is selected, the imputed date will be one day before the first vaccine dose given during that year.
- Adverse event end dates with missing day: the imputed end date will be the last day of the month (30 or 31) or the study conclusion date whichever comes first.
- Adverse event end dates with missing day and month: the imputed end date will be the last day of the year (31st of December) or the study conclusion date whichever comes first.

All incomplete concomitant medication/vaccination start/end date will follow the rules above.

10. ANNEXES

10.1. Business rules for standard data derivations and statistical methods

This section contains standard rules for data display and derivation for clinical and epidemiological studies.

10.1.1. Attributing events to vaccine doses

The dose relative to an event is the most recent study dose given to a participant prior to the start of a given event. For example, if the start date of an adverse event is between Dose 1 and Dose 2, the relative dose will be Dose 1.

If an event starts on the same day as a study dose, the relative dose will be derived from the additional information provided in the case report form (CRF) using the contents of the flag indicating if the event occurred before or after study dose. If 'after vaccination is selected, the relative dose for the event will be the one administered on the start day of the event. If 'before vaccination is selected, the relative dose for the event will be the dose prior to this one.

10.1.2. Handling of missing data

10.1.2.1. Dates

When partially completed dates (i.e. dates missing a day and/or month) are used in calculations, the following standard rules will be applied:

- A missing day will be replaced by 15
- A missing day and month will be replaced by June 30th.

See also exceptions in section 9.1.

10.1.2.2. Laboratory data

Refer to section 5.1.2 for more details

10.1.2.3. Daily recording of solicited events

10.1.2.3.1. Studies with paper diaries

For studies using paper diaries which have questions in the CRF indicating the presence or absence of solicited events, the following rules are applicable:

• Denominators for the summary of administration site (or systemic) solicited events will be calculated using the number of participants who respond "Yes" or "No" to the question concerning the occurrence of administration site (or systemic) events.

- When a specific solicited event is marked as having not occurred following a specific study dose (i.e. SDTM CE.CEOCCUR=N for the specified post-dose period for the event in question), all daily measurements will be imputed as Grade 0.
- When a specific solicited event is marked as having occurred following a specific study dose (i.e. SDTM CE.CEOCCUR=Y for the specified post-dose period for the event in question), any missing daily recordings will be given imputed values to allow them to contribute to the 'Any' rows but not to specific grade rows of the solicited event summary tables.
- When the occurrence of a specific solicited event is not present (i.e. SDTM CE.CEOCCUR is neither Y nor N for the specified post-dose period for the event in question) but the group of solicited events (administration site or systemic) is marked as having occurred (i.e. SDTM CE.CEOCCUR=Y), all missing daily recordings will be given imputed values to allow them to contribute to the 'Any' rows but not to specific grade rows of the solicited event summary tables.

The following table shows how participants contribute to each category for a specific solicited event over the Day X to Day Y post-dose period:

Solicited event category	Participants included in the calculation of the numerator
Any	All participants with at least one occurrence of the adverse event at grade 1, grade 2, or grade 3 between Day X and Day Y or with the adverse event marked as present and at least one missing daily recording between Day X and Day Y
At least grade 1	All participants with at least one occurrence of the adverse event at grade 1, grade 2, or grade 3 between Day X and Day Y
At least grade 2	All participants with at least one occurrence of the adverse event at grade 2 or grade 3 between Day X and Day Y
At least grade 3	All participants with at least one occurrence of the adverse event at grade 3 between Day X and Day Y

10.1.2.4. Unsolicited adverse events

Unsolicited adverse event summaries are including serious adverse events unless specified otherwise.

Missing severity, relationship with study vaccine, and outcome of unsolicited adverse events will not be replaced and will appear as 'UNKNOWN' when displayed in a statistical output.

10.1.3. Data derivation

10.1.3.1. Age at first dose in years

When age at first dose is to be displayed in years, it will be calculated as the number of complete calendar years between the date of birth and the date of first dose. For example:

DOB = 10SEP1983, Date of first dose = 09SEP2018 -> Age = 34 years

DOB = 10SEP1983, Date of first dose = 10SEP2018 -> Age = 35 years

In this study, we will collect only the year of birth. The rules for handling missing day and/or month in the DOB are given in section 10.1.2.1.

Since only the year of birth will be collected in the eCRF, there might be some discrepancies between the age computed using standard derivation rules and the age category used in SBIR for the minimization.

Therefore, for the analysis by age, the age categories defined in Table 4 will be determined according to the information entered in SBIR (variable AGEGRP in SDTM SUPPDM), except for "≥65 YOA" category which will be obtained using the derived age because this category is not used in SBIR for minimization

10.1.3.2. Temperature

Temperatures will be presented in degrees Celsius (°C). Temperatures reported in degrees Fahrenheit (°F) will be converted as follows:

Temperature (Celsius) = ((Temperature (Fahrenheit) - 32) x 5)/9

10.1.3.3. Numerical serology results

Numerical serology results will be derived from the content of IS.ISORRES in the SDTM dataset. For humoral assays with a specific cut-off, the following derivation rules apply:

IS.ISORRES	Derived value
"NEG", "-", or "(-)"	cut-off/2
"POS", "+", or "(+)"	cut-off
"< value" and value is <= assay cut-off	cut-off/2
"< value" and value is > assay cut-off	Value
"> value" and value is < assay cut-off	cut-off/2
"> value" and value is >= assay cut-off	Value
"value" and value is < cut-off	cut-off/2
"value" and value is >= cut-off and value is <=ULOQ	value
"value" and value is > ULOQ	ULOQ*
All other cases	Missing

*This rule will be used to compute descriptive statistics (GMTs, fold increase etc).

10.1.3.4. Geometric mean titres (GMTs) and concentrations (GMCs)

GMT or GMC calculations are performed by taking the inverse logarithm of the mean of the log titre or concentration transformations. Non quantifiable antibody titres or concentrations will be converted as described in section 10.1.3.3 for the purpose of GMT/GMC calculation. Cut-off values are defined by the laboratory before the analysis.

10.1.3.5. Onset day

The onset day for an event (e.g. AE, concomitant medication/vaccination) is the number of days between the last study dose and the start date of the event. This is 1 for an event occurring on the same day as a study dose (and reported as starting after study dose).

10.1.3.6. Duration of events

The duration of an event with a start and end date will be the difference between the start and end date plus one day, i.e. an event that starts on 3 March 2018 and ends on 12 March 2018 has a duration of 10 days.

The duration of solicited events will be calculated as the sum of the individual days with the event reported at grade 1 or higher or reported as missing ("NOT DONE"), during the solicited event period. The duration of solicited events ongoing beyond the solicited period will be calculated as end date – start date + 1. The goal of this change was to align this text with the standard programs.

10.1.3.7. Counting rules for combining solicited and unsolicited adverse events

For output combining solicited and unsolicited adverse events, all serious adverse events will be considered systemic events since the administration site flag is not included in the expedited adverse event CRF pages. Unsolicited adverse events with missing administration site flag will also be considered systemic.

Multiple events with the same preferred term which start on the same day are counted as only one occurrence.

In case a solicited event is worsening to Grade 3 after the solicited period, it should be reported only in the following table.

Summary of grade 3 adverse events (solicited and unsolicited) within 30 days following each dose and overall

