10.3.9.3. Medically attended visits

For each solicited and unsolicited adverse event the participant experiences, the participant will be asked if he/she received medical attention defined as hospitalization, or an otherwise unscheduled visit to or from medical personnel for any reason, including emergency room visits. This information will be recorded in the eCRF.

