5.4.4. Safety analysis

Primary vaccination and revaccination dose:

The safety analysis will be performed on the ES. A descriptive analysis by group, for the 3 groups pooled up to Month 12, for the RSV_flexible revaccination and RSV_1dose groups pooled vs RSV_annual group for Month 13, Month 18 and Month 24, and by group from Month 25 up to study end, will present a summary of:

- The number and percentage of participants with at least one administration site event (solicited and unsolicited), with at least one systemic event (solicited and unsolicited) and with any AE during the 4-day or 30-day follow-up period will be tabulated with exact 95% CI after each dose. The same computations will be done for Grade 3 AEs, and for Grade 3 non-serious AEs and for AEs resulting in medically attended visit.
- The number and percentage of participants reporting each individual solicited administration site event (any grade, Grade 3 and resulting in medically attended visit) and solicited systemic event (any grade, Grade 3 and resulting in medically attended visit) during the 4-day follow-up period (i.e., on the day of vaccination and 3 subsequent days) will be tabulated for each group after each dose.
- For fever, the number and percentage of participants reporting fever by half degree (°C) cumulative increments during the 4-day follow-up period (i.e., on the day of vaccination and 3 subsequent days) will be tabulated for each group after each dose.
- The incidence of each solicited administration site event and solicited systemic event (any grade and grade 3) will be represented graphically after each dose.

- The number and percentage of participants with any unsolicited AEs during the 30day follow-up period (i.e., on the day of vaccination and 29 subsequent days) with its exact 95% CI will be tabulated for each dose by group and by Medical Dictionary for Regulatory Activities (MedDRA) Primary System Organ Class (SOC), High Level Term (HLT) and preferred term (PT). Similar tabulation will be done for Grade 3 unsolicited AEs, for any causally related unsolicited AEs, for Grade 3 causally related unsolicited AEs and for unsolicited AEs resulting in a medically attended visit. The verbatim reports of unsolicited AEs will be reviewed by a qualified person and the signs and symptoms will be coded according to the MedDRA Dictionary for Adverse Reaction Terminology. Every verbatim term will be matched with the appropriate Preferred Term.

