- The number and percentage of participants with at least one report of SAE classified by the MedDRA Primary SOC, HLT and PTs and reported from Dose 1 up to 6 months post-Dose 1 and from revaccination dose up to 6 months post-revaccination will be tabulated with exact 95% CI. The same tabulation will be presented for causally related SAEs and fatal SAEs,.
- The number and percentage of participants with at least one report of causally related SAEs classified by the MedDRA Primary SOC, HLT and PTs will be reported after each dose and from Day 1 up to study end with exact 95% CI. The same tabulation will be presented for fatal SAEs.
- All SAEs will also be described in detail in a tabular listing.
- All AEs/SAEs leading to study/intervention discontinuation from dose 1 up to study end will be tabulated.
- The number and percentage of participants with at least one report of pIMD classified by the MedDRA Primary SOC, HLT and PTs and reported from Dose 1 up to 6 months post-Dose 1 and from revaccination dose up to 6 months post-revaccination will be tabulated with exact 95% CI. The same tabulation will be presented for causally related pIMDs
- The number and percentage of participants with at least one causally related pIMD classified by the MedDRA Primary SOC, HLT and PTs will be reported after each dose and from Day 1 up to study end with exact 95% CI.
- All pIMDs will also be described in detail in a tabular listing.
- The analyses of unsolicited AEs will include SAEs (unless otherwise specified).

The analysis of safety will also be performed by age category (age at Dose $1: \ge 65$ YOA, ≥ 70 YOA, ≥ 80 YOA, 60-69 YOA and 70-79 YOA) and region (North America, Europe, Asia).

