5.4.5. Additional considerations

- Compliance in completing solicited events information will be tabulated after each dose .
- The number and percentage of participants with at least one administration site event (solicited only), with at least one systemic event (solicited only) and with any solicited event during the 4-day follow-up period after each dose will be tabulated with exact 95% CI. The same computations will be done for Grade 3 AEs and for AEs resulting in a medically attended visit.
- The number of days with solicited events reported during the 4-day follow-up period will be tabulated for each solicited event, after each dose using descriptive statistics (mean, min, Q1, median, Q3, maximum).
- The number of each solicited events (any and Grade 3) that are ongoing beyond the 4-day follow-up period will be reported with the duration in days (mean, min, Q1, median, Q3, maximum).
- The list of solicited administration site and systemic events, and definition of intensity are described in Section 10.3.3 and 10.3.9.1 of the protocol.
- The number and percentage of participants with at least one report of SAE classified by the MedDRA Primary SOC, HLT and PTs and reported within 30 days following each vaccination will be tabulated with the exact 95% CI. The same tabulation will be presented for pIMDs.

The measurement of erythema/swelling (in mm) and fever (in °C/F) will be categorized as follows:

Grading	Erythema/swelling	Fever
0:	≤ 20 mm	< 38.0°C (100.4°F)
1:	> 20 - ≤ 50 mm	≥ 38.0°C(100.4°F) - ≤ 38.5°C(101.3°F)
2:	> 50 - ≤ 100 mm	> 38.5°C(101.3°F) - ≤ 39.0°C(102.2°F)
3:	> 100 mm	> 39.0°C(102.2°F)

Table 7Intensity grading scale for solicited events

Combined Solicited events and Unsolicited AEs

For clinicaltrials.gov and EudraCT posting purposes, a summary of combined solicited and unsolicited non-serious adverse events will be produced by System Organ Class and preferred terms and according to occurrence of each event.

Solicited events will be coded by MedDRA as per the following codes:

Solicited event	Lower level term code	Corresponding Lower level term decode
Pain	10022086	Injection site pain
Erythema	10022061	Injection site erythema
Swelling	10053425	Injection site swelling
Fever	10016558	Fever
Headache	10019211	Headache
Fatigue	10016256	Fatigue
Myalgia	10028411	Myalgia
Arthralgia	10003239	Arthralgia

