10.1.3.7. Counting rules for combining solicited and unsolicited AEs

For output combining solicited and unsolicited AEs, all SAEs will be considered systemic events since the administration site flag is not included in the Expedited Adverse Event CRF pages. Unsolicited AEs with missing administration site flag will also be considered systemic.

Multiple events with the same PT which start on the same day are counted as only one occurrence.

In case a solicited event is worsening to Grade 3 after the solicited period, it should be reported only in the following table.

Summary of grade 3 AEs (solicited and unsolicited) within 30 days following each dose and overall

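### In the combined solicited-plus-unsolicited AE tables, a CRF-driven rule bars unsolicited serious local reactions from the administration-site rows, and the late Grade 3 rule conflicts with the table of events ongoing beyond Day 4

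*SAP*

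**What the plan says.** The current text is SAP Amendment 3; Amendments 1 and 2 carry the same two rules. In Amendment 1 the first rule is worded "all serious adverse events will be considered systemic events since the administration site flag is not included in the expedited adverse event CRF pages".

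**Site classification.** Section 10.1.3.7 reads: "For output combining solicited and unsolicited AEs, all SAEs will be considered systemic events since the administration site flag is not included" on the expedited reporting pages. It then assigns unsolicited AEs with no site flag to the systemic category as well. The outputs concerned are the 4-day and 30-day summaries in 5.4.4. These count participants with at least one administration-site event, at least one systemic event, and any AE after each dose, and are repeated for Grade 3, Grade 3 non-serious and medically attended AEs.

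**Late Grade 3.** The same section adds: "In case a solicited event is worsening to Grade 3 after the solicited period, it should be reported only in the following table", naming the 30-day summary of Grade 3 AEs, solicited and unsolicited together. Section 5.4.5 plans a separate table giving the number and duration of each of the "solicited events (any and Grade 3) that are ongoing beyond the 4-day follow-up period".

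**Other places where these events appear.** Section 5.4.4 tabulates unsolicited AEs by SOC, HLT and PT, with Grade 3 and medically attended versions, and includes SAEs in them. It also tabulates participants with "at least one report of SAE classified by the MedDRA Primary SOC, HLT and PTs" and lists every SAE. Section 5.4.5 has a solicited-only administration-site summary.

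**The concern.** The reason given for the SAE rule is a missing field on a form, not a judgement about where the reaction occurred. Safety and reactogenicity of each schedule is a secondary objective. A reader comparing administration-site rows across doses would expect them to include a serious injection-site reaction, and 5.4.4 does not say that unsolicited ones are left out.

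The effect is sharpest in the medically attended row. Protocol 10.3.9.3 asks whether the participant "received medical attention defined as hospitalization, or an otherwise unscheduled visit to or from medical personnel", and Protocol 10.3.2 makes hospitalisation a criterion for an SAE. An unsolicited local reaction that is medically attended because of hospitalisation is therefore necessarily serious, and so necessarily counted as systemic.

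The late Grade 3 rule raises a different problem. An event that worsens after Day 4 is by definition ongoing beyond Day 4. Section 5.4.5 asks for it in a Grade 3 count by event, while 10.1.3.7 says to report it in another table only. Two programmers could produce different tables from the same data.

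**Working it through.** **Inputs.** Group sizes for safety are 990 (RSV_annual) and 330 (RSV_flexible revaccination), from Protocol 9.2. Exact intervals are Clopper-Pearson (SAP 10.1.5.1). The documents give no rate of serious local reactions.

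**The plan's own figures.** Section 10.1.3.7 states no number. The nearest is Protocol Table 23, the probability of at least one event, 1 − (1 − p)^n. At p = 0.10% this gives 62.86% for n = 990 (stated 62.9%) and 28.12% for n = 330 (stated 28.1%). All 30 cells reproduce to within 0.1 percentage point. If serious unsolicited local reactions truly occurred at 0.10%, an assumed rate, those would be the chances of seeing at least one. The number counted in the administration-site row would still be zero.

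**Shift per participant.** With k participants whose only local event is an unsolicited SAE, the administration-site row is too low by k/n:

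| k | n = 990 | n = 330 |
|---|---|---|
| 0 | 0 | 0 |
| 1 | 0.10 points | 0.30 points |
| 3 | 0.30 points | 0.91 points |

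The systemic row rises by the same amount, less any participants already counted there. The any-AE row does not change. These are full planned group sizes; if fewer receive a later dose, the shift per participant is proportionally larger.

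**Illustration in a Grade 3 row.** Suppose 20 of 990 participants have a non-serious Grade 3 local event. The row shows 20/990 = 2.02% (95% CI 1.24 to 3.10). Including participants whose only Grade 3 local event is an unsolicited SAE gives:

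- one more: 21/990 = 2.12% (1.32 to 3.22)
- three more: 23/990 = 2.32% (1.48 to 3.47)
- five more: 25/990 = 2.53% (1.64 to 3.71)

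The 20 and the added counts are assumptions.

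**Grade 3 against Grade 3 non-serious.** Section 5.4.4 asks for both. As far as unsolicited events go, no SAE can enter the administration-site row of either, so that row cannot differ between the two versions.

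**Where a late-worsening solicited event goes.** Take onset within Days 1 to 4 and Grade 3 first reached afterwards.

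- The individual solicited-event tables stop at Day 4, so Grade 3 is outside their window.
- The Protocol glossary makes a solicited-type event unsolicited only if its onset is outside the window, so the unsolicited Grade 3 tables by PT do not take it.
- The combined Grade 3 summary in 5.4.4 has administration-site, systemic and any-AE rows, not a row per event.
- The 5.4.5 table of ongoing events is by event and has a Grade 3 count. Under a literal 'only', the event stays in its 'any' count and drops out of its Grade 3 count.
- Read the same way, 'only' also keeps a non-serious late Grade 3 event out of the 30-day Grade 3 non-serious summary in 5.4.4, where it belongs.

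**The case against.** The strongest reply is that nothing is hidden. The SAE rule is limited to combined outputs, is prespecified and gives its reason. The reactogenicity endpoint is each solicited event within 4 days, which the individual and solicited-only tables serve without this rule. A serious unsolicited injection-site reaction within 30 days still appears under its own term in the unsolicited AE tables, including the Grade 3 and medically attended versions when it qualifies, and in the SAE tables and listing. All of that stands. It rules out the tempting reading that every serious reaction is treated as systemic throughout the report. It does not correct a site split that is wrong by rule in the combined tables.

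On late Grade 3, 'only' sits under a heading about combining event types. It may mean just which combined table takes the event, without overriding 5.4.5. That is a fair reading and probably a sensible intention, but the sentence does not say so. A reader might also infer that such events vanish by event type, or that the rule singles out local reactions. Neither is supported: the events remain in the 'any' count by event, and the rule covers fever, headache and the other systemic solicited events equally.

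A further objection concerns the remedy. Protocol 10.3.8 asks investigators to record the diagnosis and not the individual signs, so a term such as cellulitis may name no site. The documents do not show that a lookup on HLT alone would catch such cases. This stands, and the fix allows for it.

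**Conclusion.** The point holds as a misclassification confined to the combined tables, together with an unreconciled pair of instructions. By rule, unsolicited SAEs and unsolicited AEs with a missing flag cannot count as administration-site events there. Each affected participant moves a row by 0.10 points in 990 or 0.30 in 330, unless already counted in that row. No expected count can be derived from the documents, and it is probably small. The study is descriptive, so no decision threshold is at risk.

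For late Grade 3, the loss under a literal reading is the Grade 3 label by event type, for every solicited event that worsens after Day 4.

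It would go too far to say that the most severe local reactions are removed from the safety report. Protocol 10.3.9.1 keeps Grade 3 and seriousness apart, and the SAE rule concerns seriousness only. The documents also do not say whether a serious reaction recorded as solicited in the diary keeps its administration-site status in the combined tables, so the conclusion is limited to unsolicited events. The correction is still worth making, because it is cheap and uses data already coded.

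**What to change.** 1. In SAP 10.1.3.7, classify SAEs and unsolicited AEs with a missing site flag as administration-site events when the coded MedDRA term (lower level or preferred term) names an injection, vaccination or administration site. Decide terms that name no site by medical review of the verbatim before the analysis, and count the rest as systemic. Footnote the combined tables with this rule. Section 5.4.5 already codes the solicited local events to injection-site terms, so the approach fits the existing coding.
2. In the same section, limit 'only' to the choice among combined tables, and state that late-worsening events also count in the 30-day Grade 3 non-serious summary when they are non-serious. In the 5.4.5 table, grade each ongoing event by its maximum intensity over its whole course, and mark those that first reached Grade 3 after Day 4.

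The cost is a few sentences in the SAP, slightly more programming, and a short medical review of a few terms. No new data are collected.
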